Sixty percent of Canadian adults are accessible through the workplace (Government of Canada; Employment and Social Development). Thus, workplace wellness programs that include physical activity components provide a viable option to encourage employees to become more physically active. Recent studies have demonstrated that workplace wellness programs significantly improve the health status of lean as well as obese individuals⁵ with hypertension, dyslipidemia and psychological distress.⁶ Despite this information, many workplaces do not want to intrude into employee's personal lives or incur significant costs as a result of implementing evidence-based programming. In a previous study conducted by our group entitled ENCOURAGEing Workplaces, we successfully supported 54 workers to increase their total physical activity levels by 160 minutes per week through an individualized approach to physical activity prescription. This outcome stimulated our team to identify strategies to upscale the ENCOURAGE approach to influence the health behaviour of a larger number of Manitobans. Moving forward with the ENCOURAGE health promotion model, we will use *mobile health technology* to support employees to become more physically active, while offering employers a solution that can be easily implemented in a variety of contexts. We recognize the technical challenge of creating a physical activity promotion mobile application (herein referred to as the ENCOURAGE App) that is tailored for the workplace sector. Therefore, we have partnered with Tactica Interactive (<http://tactica.ca/>) to secure the programming expertise necessary to develop the app (**Appendix 1**). Tactica staff have helped us to refine the app concept and have developed a two-page description of the ENCOURAGE app that is included within this document (**Appendix 2**). Our research team previously conducted the ENCOURAGEing Workplaces project (E2014: 094) at this site and have the support of the St. Boniface Hospital executive (**Appendix 3**) and union leadership (**Appendix 4**) to conduct this new project. For the development phase of this App, we have conducted a market research survey (H2015:405) to inform the user development of a prototype version of the App, completed the testing of a proto. We are also testing the prototype version of the ENCOURAGE App in a user observation setting (H2016:097) to determine the user experience and what they liked and disliked with the App, and beta tested the App to further develop the final product. The present study will publicly release the final ENCOURAGE App product.

Trial objectives and purpose

The objectives of this study are to determine if the final product ENCOURAGE App can over a 6 month period:

- 1) Enhance physical activity levels; and,
- 2) Improve cardiovascular health risk;

Trial design

The public release of the ENCOURAGE App will involve two phases (Figure 1):

- 1) The recruitment of 300 individuals through the App. Any user will be able to download the ENCOURAGE App through the iTunes Store or Google Play. Note that when participants download the App, they are not automatically enrolled in the study. Participants will be prompted, after downloading the App, with a brief description of the study, as well as a pre-screening tool will be used to determine eligibility (see below for inclusion/exclusion criteria). Users will be asked via a textbox to determine if they wish to participate in a research project. Users will be asked to participate in a *time series quasi-experimental design* study to determine if the ENCOURAGE App can support participants to increase their physical activity levels over a 6 month period. The App uses a time management technique (i.e., Pomodoro technique) as a strategy to provide prompts for users to engage in an activity. The App can be customized by the users to set prompts at intervals that fits into their schedule. For example, these activities can range from a stretching activity (e.g., a neck stretch), a standing activity (e.g., stand and read), or a physical activity (e.g., fill up the printer with paper, do a squat). Additionally, the App will use Behavior Change Techniques as a way to support participants as they reduce their sedentary behavior and improve their physical activity levels.⁷ The App uses a series of Behavior Change Techniques shown to be effective in promoting a more physically active lifestyle.^{8,9} Users will also provide feedback regarding the App using an *experience sampling approach*, which uses a list of questions to guide user feedback (**Appendix 5**). Additionally, we will use *Flurry Analytics* (<http://www.flurry.com/>) to measure, track, and analyze the ENCOURAGE App performance, and aggregate-level user activity within the App. Specifically, we wish to determine the number of user sessions within the App, frequency of use, session length, user events, technical data and errors, and user geographic distribution. For a more detailed description of the experience sampling and Flurry Analytics approaches, see **Appendix 6**.
- 2) The recruitment of a sub-sample of 60 participants who live in Winnipeg, MB which will be drawn from the larger sample of 300 participants and by advertisement. In addition to completing all the components listed above from the recruitment of 300 participants, they will be also asked to wear a physical activity monitor, called an accelerometer.

Inclusion and exclusion criteria

Inclusion criteria:

- Male and female employees 18-70 years old
- Self-identify as being physically inactive in the last 3 months (less than 150 minutes of moderate-vigorous physical activity per week)
- Ready to adopt a more physically active lifestyle based on the Transtheoretical Model¹⁰
- Specific to the sub-sample of 60 participants: Live in Winnipeg, MB

Exclusion criteria:

- Individuals who do not have a personal mobile phone
- Any physical limitations that would not allow a person to engage in physical activity
- Any cognitive limitations that would not allow a person to consent for the study
- Specific to the sub-sample of 60 participants: Those who live outside of Winnipeg, MB.

To our knowledge, no characteristics of the participants make them especially vulnerable or require extra precautions to administer the user observation study. Participants will be healthy volunteers able to provide informed consent.

Participant recruitment

Recruitment of participants involves two phases (Figure 1):

- 1) Recruitment of 300 individuals who download the ENCOURAGE App the iTunes Store or Google play and choose to enroll in the study. Users will be asked via a textbox to determine if they wish to participate in a research project. A description of the project, as well as an electronic consent form will be provided prior to enrolment through Survey Monkey. In order to track participants in the study, we will be asking for their e-mail addresses, their date of birth, and first and last name initials.
- 2) Recruitment of 60 individuals who live in Winnipeg, MB to wear an accelerometer. We will employ a convenience sampling approach, where participants who are already using the App and participating in the study (i.e., the 300 participants described above) will be asked to participate if they live in Winnipeg. Additionally, we will employ a convenience sampling approach at the St. Boniface Hospital, University of Manitoba, and Tactica Interactive. Participants will be contacted via e-mail. First, we will use an e-mail approach to contact participants. The e-mail approach will provide contact information for potential participants to reach research staff to facilitate the recruitment and consent of participants at a mutually agreeable location. Secondly, we will use a poster advertisement approach (**Appendix 7**) to facilitate recruitment. Posters will be placed around the St. Boniface Hospital, University of Manitoba, and Tactica Interactive. In total for the sub-study, more than 12,000 staff members at the St. Boniface Hospital, 8,700 faculty/staff, at the University of Manitoba, and Tactica Interactive will be accessible, including:
 - Nurses and Nurse Practitioners;
 - Physicians;
 - Property Management (electrical, carpentry, mechanical);
 - Administrators and clerical support staff; and,
 - Researchers
 - Software developers

Study procedures

Large study procedures:

After participants choose to participate in the study, participants will be asked to complete a series of questionnaires at baseline, one week and every month for a total of six months (i.e., 8 different

occasions). The questionnaires (**Appendix 8**) will take approximately 30-45 minutes to complete and comprise of the following:

- 1) Demographics
- 2) Depressive symptoms with the Patient Health Questionnaire-9
- 3) Physical activity using the Godin Leisure Time Exercise Questionnaire
- 4) Cardiovascular health risk using the Cardiovascular Health in Ambulatory Care Research Team (CANHEART) questionnaire
- 5) Occupational Sitting with the Occupational Sitting and Physical Activity Questionnaire
- 6) Self-efficacy levels for physical activity and reducing sedentary time with the Exercise Self-Efficacy Questionnaires and Self-Regulatory Efficacy to Manage Sedentary Behavior questionnaire
- 7) Confidence levels for reducing sedentary behaviors with the Barrier Self-Efficacy to Reduce Sedentary Behavior and Self-efficacy to Reduce Total Daily Sedentary Time questionnaires.
- 8) Physical activity levels at the workplace with the Workplace Sitting Breaks Questionnaire

Research participants will be prompted within the App to a hyperlink to complete the research questionnaires on Survey Monkey. In order to track individual research participant responses The links are as follows:

- 1) Description of the study/eligibility form, consent to participate, and baseline questionnaire: <https://www.surveymonkey.com/r/L3KDHRQ>
- 2) 1 week survey: <https://www.surveymonkey.com/r/L39CZB5>
- 3) 1 month survey: <https://www.surveymonkey.com/r/L3J2M67>
- 4) 2 month survey: <https://www.surveymonkey.com/r/L3SKXGH>
- 5) 3 month survey: <https://www.surveymonkey.com/r/L3MDLCF>
- 6) 4 month survey: <https://www.surveymonkey.com/r/L3FLMWG>
- 7) 5 month survey: <https://www.surveymonkey.com/r/L3B28KX>
- 8) 6 month survey: <https://www.surveymonkey.com/r/L3P9FGC>

[figure not shown]
Participants will also be asked on two separate occasions over the 6 month period to document their experiences using an experience sampling approach. A list of questions used are in **Appendix 5**.

Sub-study procedures:

Participants from Winnipeg, MB who choose to enroll in the sub-study will complete the study procedures for the large study and will also be asked to meet with research staff to obtain consent for the smaller study and will be asked to wear an accelerometer for 7-day periods at baseline and every month for 6 months (i.e., 7 different occasions). The research appointments will last approximately 30 minutes each.

See below for a figure overviewing the flow of the study.

Figure 1. Study flow chart

Assessment of Safety

Since this is not a drug study, rescue medication is not warranted. Should any participant experience adverse effects as a consequence of participation in the study, they will be excluded from the study and receive routine clinical care. All serious adverse events as well as death due to any cause or cardiovascular death will be reviewed by the medical monitor within 24 hrs of becoming aware of events. Any Serious Adverse Events will be reported to the University of Manitoba Health Ethics Boards and St. Boniface Hospital.

Statistics

Sample Size

The primary outcome for this time series quasi-experimental study is a change in moderate-vigorous physical activity within the subset of 60 participants. When doing a pre/post power analysis, an estimate of correlation between the pre and post measurements is required. We assumed a high correlation of 0.8 between measurements. Under this assumption, the sample size needed to detect a 20 minute/week increase for moderate-vigorous physical activity (Mean \pm SD; Pre: 72 \pm 64 min/week; Post: 92 \pm 86 min/week) is n=44 for with a two tailed α of 0.05 and power of 80%. Even so, we will recruit 60 participants to account for the possibility of drop out. If we assume a moderate correlation of 0.5 between Pre-Post, the sample size of 60 will still be large enough to detect a change in total physical activity (Pre: 1240 \pm 182 min/week; Post: 1402 \pm 455 min/week).

Study Data

For the experience sampling and Flurry Analytics approach to this study, data from participants at the aggregate level using the mobile App will be analyzed to categorize responses, generate frequency charts, and define themes

For the quasi-experimental design, a one-way repeated measures ANOVA or Mann-Whitney Test will be used to examine changes in breaks in sedentary time and other continuous outcome measures from baseline to 1 week, 1-month, 2-month, 3-month, 4-month, 5-month, and 6-month depending if the data are normally distributed. Categorical variables will be compared using a Chi-Square test. Relationships between variables will be assessed using Pearson or Spearman correlations, as well as multivariable linear or logistic regression.

Informed consent

The written consent form will be reviewed by the Health Research Ethics Board at the University of Manitoba prior to the initiation of the study. The consent form will describe the study procedures, risks and possible benefits, and will be reviewed by the participant prior to their enrollment in the study. Each participant will be asked to read the consent form and will be provided an opportunity to ask questions before they are enrolled. All participants will be required to provide written consent prior to initiation of study procedures. The consent form will be signed and dated by the participant and will be counter-signed by the researcher who conducted the informed consent process. The researcher will retain the original signed consent form and a copy of the form will be provided to the participant.

Study participants may decline to participate in the study or withdraw from participating at any time throughout the course of the study. Participants are free to withdraw from the study at any time upon

request by contacting any individual from the research team, or directly by contacting [name] (email: [contact]).

Ethics

A full submission will be made to the University of Manitoba Health Research Ethics Board and the St. Boniface Hospital Research Review Committee for written approval of the study prior to implementation. Any amendments where necessary, will be submitted for review and approval prior to implementation. Study status will be reported annually. A final study notification will be forwarded at completion of the study or in the event of early termination. The tenets of Good Clinical Practice will also be followed. Subjects are free to withdraw from the study at any time without affecting their right to ongoing medical care.

Deception

Deception will not be used in this study.

Feedback/Debriefing

At the conclusion of the user observation session, participants will be thanked and given an opportunity to provide their contact information if they would like to receive a summary of the overall study findings. Participants will also be provided an opportunity to indicate if they are willing to be contacted for future research studies.

Risk and Benefits

The risks with participating in this study are considered to be minimal. There is a very minor risk associated with participating in physical activity, but the benefits of participating in physical activity significantly outweigh the minimal risks.

Despite best efforts to keep personal information confidential, absolute confidentiality cannot be guaranteed for the participant. If a participant chooses not to allow contact for further research, their data will remain anonymous. If a participant chooses to allow contact for further research and indicates they would like to receive a report of the overall study findings, they must identify themselves so that they can be contacted. However, this contact information will be separated from all research data. A password protected spreadsheet located on a secure drive in the principal investigator's office containing the participant's name and contact information will be maintained separate from all other research data. Neither participants' name nor contact information will appear in any publications stemming from this research.

There may or may not be direct benefit resulting from participation in the study. Potential benefits of participation include the opportunity to influence the development of a workplace wellness initiative that more appropriately addresses the unique needs of an employee.

Anonymity or Confidentiality

With regards to use of the ENCOURAGE App, while there can never be absolute guarantees regarding unauthorized access to a system or data, there are several key security risk mitigations that can be put into place to greatly help in protecting private information. Any aggregate usage data will not be directly attributable to a device or individual. Data that is intended to be shared with researchers

will be coded or anonymized, and will be a select subset of data transferred over a secure encrypted connection. Any personal information will be stored only locally on the device, and no personally identifiable information will be shared with researchers or pushed to a cloud system. The App will be delivered through a website (<http://www.encourageapp.com>) as a signed binary, and any content remotely served to the application will restrict content and markup, as will be served as read only data to prevent any opportunities for HTML or SQL injection.

Information gathered in this research study may be presented at conferences or published in a peer-reviewed journal.

All data (i.e. notes, questionnaire data) will be labeled with a unique identification code. Briefly, a code (i.e. EABPR01, EABPR02, etc.) will be used to label the questionnaire package. Data linking the participant identification code with the participant's name and contact information (if provided during informed consent process) will be maintained in an independent, password protected spreadsheet. Information gathered in this research study may be presented at conferences or published in a peer-reviewed journal. Any publications resulting from the study will present themes that emerge from the experience sampling and quotes that support the themes. If a reference is made to a direct quote, pseudonyms will be used in place of the participant or organizational name in order to protect anonymity. Despite best efforts to keep personal information confidential, absolute confidentiality cannot be guaranteed for the participant. The results will also be used to generate a report to inform the development of the final version of the ENCOURAGE app.

If a participant chooses not to allow contact for further research, their data will remain anonymous. If a participant chooses to allow contact for further research, they must identify themselves so that they can be contacted (e.g. name, email, phone). However, this contact information will be separated from all other questionnaire data. Neither the participants' name nor contact information will appear in any publications stemming from this research.

When the project is completed, identifying data file (i.e. Excel spreadsheet) stored on a secure computer in the principal investigator's office will be destroyed after a period of 7-years. A password-protected USB storage device with research data will also be stored in a locked filing cabinet in [name] office location for 7-years, where only the principal researcher will have access to this data. After this seven-year period, all electronic data will be permanently deleted and the computer hard drive will be re-formatted. Anonymous hard copy data will also be destroyed after 7-years using similar confidential waste procedures.

Compensation

For the larger study, research participants will be entered into a draw to win one of ten (10) \$20 gift cards to either Starbucks or Chapters-Indigo. As such, research participants will be asked to provide their e-mail addresses to indicate if they have won a gift card.

Dissemination

The qualitative information gathered from the experience sampling will be disseminated into a final study report. The information obtained from this study will be used to generate a report that will inform the utility of the ENCOURAGE App. Broad themes that emerge from the comments of multiple study participants will be summarized and any direct quotes that are extracted to support themes will not reveal names or other identifying information. All information that may reveal personal identifiers will be removed prior to data analysis in order to protect anonymity.

Financing

The study is being financially supported by a Heart and Stroke Foundation Manitoba Primary Prevention Challenge Grant

References

1. Hutchinson, A. D. & Wilson, C. Improving nutrition and physical activity in the workplace: a meta-analysis of intervention studies. *Health Promot Int* **27**, 238–249 (2012).

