Appendix 6: Description of experience sampling and Flurry Analytics

Experience sampling:

Experience sampling and marketing validation is a strategic research technique for uncovering user needs and wants. Users are interrupted at defined intervals to note their experience in real-time. The following steps will be taken to gather experience sampling data:

1. Define experience sampling questions based on criteria that focusses on repeated behaviour and avoids yes/no questions, quantity-based answers or opinions.
2. Categorize responses, clean data, adjust categories
3. Generate frequency charts and define themes

Flurry Analytics description

Flurry Analytics is an industry standard that allows researchers and organizations to understand what components of the App the users are most engaged with. It is important to note that individual-level data will not be linked to the user's personal information. Flurry Analytics collects data at the aggregate level. User's IDs are anonymized and are created to pair with the user's device and the server. It is important to note that the user's ID is only known by the server.

Flurry analytics can measure user sessions, frequency of use, session length. Analytics can also determine if the users are progressing through the app as intended, data describing the number of times a specific module of the app was started and how long the user stayed engaged with each module. Flurry is an industry standard analytics tool that measures, tracks and analyzes app performance, user acquisition and activity. Flurry provides a deep understanding of app performance metrics and user behaviour. The following information will be gathered:

- **User sessions**
 - The number of unique users and total number of user sessions - ie 10,000 unique users and 25,000 sessions.
- **Frequency of use**
 - Session frequency distribution for daily, weekly and monthly time periods - ie in a weekly period 2,000 users had 1 session, 4,000 users had 2-3 sessions, 1,500 users had 4-6 sessions
- **Session length**
 - Session length distribution and mean session length - ie median session length is 1.6 minutes, 1,000 users used the app 0-1 min, 2,000 users for 1-3 min, 1,000 users 3-5 min
- **User events**
 - Custom events defined within the app - ie 10,000 users clicked "Save" - or users clicked "Save" and average of 2.6 times per session
- **Technical data and errors**

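### Accelerometer subset: participants recruited from existing App users have their baseline wear week after App exposure began, so any early effect dilutes the Protocol's primary pre/post change

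*Protocol*

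**What the plan says.** The Protocol's Sample Size section sets the endpoint: "The primary outcome for this time series quasi-experimental study is a change in moderate-vigorous physical activity within the subset of 60 participants". It is sized as a pre/post comparison with no comparison group.

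The Trial design section says the 60 are "drawn from the larger sample of 300 participants and by advertisement". No split between the two sources is given. Participant recruitment, item 2, describes the first source: "participants who are already using the App and participating in the study (i.e., the 300 participants described above) will be asked to participate".

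Under Sub-study procedures these people then "meet with research staff to obtain consent for the smaller study and will be asked to wear an accelerometer for 7-day periods at baseline" and monthly for six months. The Informed consent section adds: "All participants will be required to provide written consent prior to initiation of study procedures".

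On usage data, the Anonymity or Confidentiality section states: "Any aggregate usage data will not be directly attributable to a device or individual". Appendix 6 agrees: "Flurry Analytics collects data at the aggregate level". The Anonymity section also mentions a coded or anonymised subset of data for researchers, without saying what it holds.

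Neither the Protocol's Study Data section nor the SAP uses recruitment route, prior exposure or days of use. The SAP names a different primary outcome, the number of breaks in sedentary time from baseline to 1 month, and gives no instrument for it.

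**The concern.** In an uncontrolled pre/post design, the estimated effect is the follow-up value minus the baseline value. The baseline is meant to show activity without the App. Someone recruited because they already use the App cannot supply that value once the wear week is tied to a later consent visit.

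If the App raises activity in its first days or weeks, part of the effect is already in the pre value and is subtracted out. The estimate is then too small and a real effect may be missed. If an early novelty effect fades, the measured change could be smaller still, or negative. If the App has no early effect, this mechanism does no harm. A positive App effect would be hidden by it, not created.

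An accelerometer week before App use cannot be obtained afterwards, so the point has to be settled before enrolment.

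**Working it through.** **1. Order of events for existing users.** App use has begun (Participant recruitment, item 2). They then meet staff and give separate consent (Sub-study procedures). Written consent precedes study procedures (Informed consent). Baseline wear therefore comes after first App use. No visible text provides a limit on prior use, a washout or a pre-App wear week for them.

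**2. Order of events for advertised recruits.** The poster (Appendix 7) lists App installation at the first visit, and accelerometer wear, but the list is not a sequence. Figure 1 is not shown. The order is open.

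**3. The plan's own sample size.** Inputs from the Sample Size section: SDs 64 and 86 min/week, change 20 min/week (72 to 92), two-sided alpha 0.05, power 80%, and "We assumed a high correlation of 0.8 between measurements".

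SD of change = √(64² + 86² − 2 × 0.8 × 64 × 86) = √2685.6 = 51.82 min/week.

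A paired t test needs n = 55 (53 by the normal approximation), against 44 stated. That mismatch is a separate matter. What counts here is the reserve: 60 completers give 83.7% power.

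**4. Illustration of dilution.** The documents give neither the share f of the 60 who are existing users nor the fraction g of the effect present at their baseline. Both are assumptions. Expected change = 20 × (1 − f × g). Power is from the paired noncentral t, n = 60, with the SD of change held at 51.82.

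| f × g (example) | Expected change, min/week | Power |
|---|---|---|
| 0 | 20 | 83.7% |
| 2.5% (10% of sample × a quarter of effect) | 19.5 | 81.8% |
| 5% (10% × half) | 19 | 79.8% |
| 12.5% (25% × half) | 17.5 | 73.0% |
| 25% (half × half) | 15 | 59.7% |
| 50% (half × all, upper end) | 10 | 31.3% |

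Mixing two routes also adds variance f(1 − f)(20g)² to the change. This matters little: 79.8% becomes 79.6% at 10% × half, and 59.7% becomes 59.3% at half × half. The correlation matters more. At an assumed 0.9 the SD of change is 39.81, and a 15 min/week change would have 81.9% power.

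**5. Cost of restricting to unexposed baselines.** At the full 20 min/week and r = 0.8, without replacement: 54 analysed (10% left out) gives 79.5%, 45 (25%) gives 71.6%, and 30 (50%) gives 53.3%.

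**The case against.** The strongest reply is that the size is entirely assumed, the direction is conservative, and the loss may be only 2 to 4 percentage points (81.8% or 79.8% against 83.7%). All of that stands. It limits the size of the point but does not remove it. The Protocol's first objective is to learn whether the App enhances physical activity, and an estimate that is too small does not serve that. The reserve is also thin: a 5% average carry-in takes power just below 80% before any dropout, and the 60 were meant to absorb dropout.

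A reader might infer several stronger things that the documents do not support:

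- **That the size of the problem can never be examined.** Existing users complete the large-study baseline survey through the App, and their responses are tracked. Its date gives a latest bound on first use, hence a minimum exposure at the wear week. The leisure-time exercise and sitting-breaks questionnaires at enrolment, one week and monthly allow a partial check of early drift. They are self-reported and also follow download.
- **That a first-use date will certainly be missing.** None is visible, and the analytics are aggregate. But this rests on silence: the coded data subset is unspecified, and Figure 1 and the demographics items are not shown.
- **That all 60 baselines are affected.** For advertised recruits this is not established.
- **That the SAP's primary outcome has the same flaw.** It does only if breaks are taken from the accelerometer. The Protocol also contains a workplace sitting-breaks questionnaire.

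**Conclusion.** The point holds for participants recruited from existing App users: their pre value in the Protocol's primary change in moderate-vigorous activity is measured after exposure began. With no control group, any early App effect biases their change toward zero. This follows from the recruitment and consent text and needs no assumption about Figure 1.

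The size is unknown. On assumed values, power with 60 completers falls from 83.7% to 79.8% at 5% average carry-in and to 59.7% at 25%. The 31.3% case needs half the sample to have the full effect at baseline and should be read as an upper end, not an expectation. All figures rest on the Protocol's SDs, r = 0.8, no dropout and a constant SD of change, and apply only to the Protocol's primary outcome.

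This should be fixed before enrolment. It calls for better timing, one recorded date and a prespecified analysis. It does not require dropping existing users from the study.

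**What to change.** 1. **Participant recruitment and Sub-study procedures.** For participants recruited by advertisement, state that the 7-day baseline wear is completed before the App is first used or activated. Say how the baseline survey, which is reached through a prompt in the App, fits that order.
2. **Sub-study consent visit.** Record recruitment route and date of first App use for every participant.
3. **Study Data section and SAP.** Keep all 60 in the analysis. Prespecify reporting of the accelerometer change by route and by days of App use before baseline, with a sensitivity analysis limited to participants whose baseline wear preceded first use. State that the all-60 estimate is likely diluted if the App acts early. State also whether the SAP's breaks outcome comes from the accelerometer, so that it is clear whether the same analysis is needed there.

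Cost: a short amendment, about one week's delay to App start for advertised participants, possibly one extra contact each, two data fields and one table. The restricted analysis has less power, as shown above, and should be presented as supportive.

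Optional, for the sponsor to weigh: fill more of the 60 places by advertisement. This leaves fewer exposed baselines but may slow recruitment, and it narrows the sample to the named employers, one of which develops the App. If existing users were kept and also replaced, wear weeks would rise; 15 such users would add 15 × 7 = 105.
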